2.2. Overview

[figure not shown]

Figure 1: Flow chart of study organisation

This study will assess the accuracy, effectiveness and efficiency of PO in a delayed-type cross-sectional accuracy study. First, PO will be performed soon after delivery in all cases, which will have the advantage of identifying potentially serious low oxygen saturations in a timely fashion before symptoms are apparent. Integrating PO into the assessments performed routinely by the midwife when mother and baby are transferred from the delivery suite to the post-natal ward will make this design practicable and achieve maximum recruitment. Testing will occur early but over a range of times within the first 24 hours after birth (usually within 3-6 hours) or before discharge, allowing analysis of the optimum time for PO screening. After conducting PO, we will use different reference standards for test positive and test negative cases: echocardiography for the former and follow-up for the latter.

In this design, it would be unlikely that the subsequent clinical examination could be performed independently of the PO results, as midwives would want to alert the medical staff to a low saturation. This precludes a direct comparison of PO against clinical examination, as the latter would be prone to work-up bias. This comparison will be made through decision-analytic modelling using unblinded and historical data for input and appropriate sensitivity analyses conducted.

Clearly, in the presence of a feasible and accurate CHD screening strategy, there will be a need to consider the cost-effectiveness. The cost-effectiveness of PO in combination with postnatal clinical examination will be evaluated against examination alone and examination and antenatal screening, in a model-based analysis. Two systematic reviews of the performance of antenatal screening for CHD in first trimester (4) and second trimester (19) have been performed. Data on this group will be collected as part of our study. Using directly obtained information on outcomes and costs from a large number of babies in a real-life setting, the implications of all methods of identification of CHD will be modelled, thereby improving the generalisability of the results.

2.3. Test accuracy study design

A test accuracy study is different to an effectiveness study in that randomisation of subjects is not involved. An outline of the test accuracy study is shown in Figure 2. It is designed to generate a comparison of measurements obtained by index tests with those obtained by reference standards. In this way the accuracy of index tests can be estimated. A reference standard is a test that confirms or refutes the presence or absence of disease beyond reasonable doubt. Therefore it is sometimes also known as the gold standard. PO is the index test whereas the reference standard will be the identification of CHD cases up to one year through echocardiography, databases maintained by the West Midlands congenital anomaly register (CAR), regional cardiology referral unit, regional perinatal mortality survey, hospital information departments and, if necessary, READ codes of primary care trusts.

[figure not shown]

Figure 2 Flowchart of test accuracy study of PO as a screening tool for CHD in newborns

2.4. Large, simple study: minimal extra workload

In order to obtain the large number of patients necessary for the reliable evaluation of the PO test, the study will need the participation of more than one centre. To make these practicable, study procedures need to be kept simple, with the minimal extra workload placed on participating clinicians, beyond that required to manage their patients. This will be achieved by simple entry procedures, early consent of women, the use of standard local testing regimens, minimising documentation and streamlining data collected procedures. Regular newsletters will keep collaborators informed of study progress, and regular meetings will be held to report progress of the study and to address any problems encountered in the conduct of the study.

2.5. Setting

The setting will be 6 large maternity units in the West Midlands region. These units are based in the following hospitals: Birmingham Women's, Heart of England, City (Birmingham), New Cross (Wolverhampton), University Hospital of Coventry & Warwickshire (Coventry), and Royal Shrewsbury. These units serve a large, socio-economically and ethnically diverse population, which will aid generalisability of findings and have a large total number of deliveries (over 30,000 per annum). The units also represent the spectrum of obstetric settings, from a busy district general hospital to a specialised tertiary referral centre.

3. ELIGIBILITY

3.1. Eligibility criteria for the test accuracy study

The following inclusion / exclusion criteria will be used:

3.1.1 Inclusion criteria

Mother	Given written informed consent for screening and follow-up through databases
Baby	Gestational age ≥ 35 weeks Asymptomatic at birth, regardless of antenatal risk factors or ultrasound findings

3.1.2 Exclusion criteria

Mother	Unable to give consent through incapacity, inability to speak English and lack of interpreter
Baby	Symptoms of cardiovascular abnormalities at birth

3.1.3 Inclusion of babies with suspected CHD from antenatal ultrasound

Babies suspected of having CHD, following antenatal ultrasound, will be included in the study. These pregnancies will be managed under the care of a consultant and will be transferred shortly after birth to a neonatal unit, where they will routinely have PO monitoring. The first reading, prior to any therapy or oxygen administration, will be recorded for the purposes of the study (provided the baby is asymptomatic at the time).

The evidence from the review about the accuracy of midtrimester fetal ultrasonography (19) showed that this antenatal test was not without error and it did not lend support to its routine use among unselected and low risk populations. In fact, practice concerning the intensity of such screening across the UK varies considerably, as does associated test performance. The West Midlands region, however, has an active, specialist-based fetal echocardiography screening programme for high-risk mothers, which detects a significant proportion of fetuses with CHD. Most babies born with a positive antenatal test result are

asymptomatic at birth, would comfortably meet all our inclusion criteria (see sections 3.1.1 and 3.1.2), and would have been eligible for mass screening with PO, regardless of antenatal screening, whether risk or ultrasound based. In babies with positive antenatal scan, PO is currently routinely carried out after birth on admission to the neonatal unit, so it would be unwise to disregard this information. There is no risk of introducing bias in PO estimation due to prior the suspicion of CHD as PO is an objective test. By including this subgroup, the overall CHD prevalence will be increased, thereby increasing the power and precision. It will allow the opportunity to explore variation in test accuracy in different population spectra and will help determine the added value of PO over and above what is achieved by antenatal screening. This information will be critical input into the decision-analytic model.

3.2. Recruitment of participants

Although PO will be introduced as a routine post-natal test, consent will still need to be obtained from each mother for the purposes of the study. Ideally consent is sought under unhurried circumstances, when entry criteria are fulfilled. These two issues may not be easily satisfied simultaneously in this study, as the setting involves obtaining PO readings in the first few hours of the baby's life. Consent will be sought in stages:

- A patient information leaflet will be given to all pregnant women at the time the mid-trimester ultrasound scan, or at any time after the scan but before birth, by the community or antenatal clinic midwives. The leaflet will also be made generally available and prominently displayed in various areas within the participating hospitals and their community antenatal clinics. This leaflet will be available in different local languages to reflect the ethnic communities at each centre.
- The leaflet will emphasise that PO is being introduced for routine use in the participating hospitals for the duration of the study, but that parents are entitled to choose whether or not they want their baby screened. Parents will be advised to discuss the study with the community or antenatal clinic midwife if they have any questions; and the phone number of the local coordinating midwife for the study will be provided.
- A coloured sticker confirming that the leaflet has been passed to the mother will be attached to the front of her notes. A copy of the information leaflet and consent form will be included in the hand-held notes. Any parent declining PO before delivery will have this recorded in the maternity notes.
- The consent form can be signed by the mother at any point before delivery and countersigned by the community or antenatal clinic midwife. At the time of testing, the consent will be reconfirmed verbally and any change recorded on the consent form.

Where necessary, appropriate interpreters will be asked to aid discussion relating to study participation. Some of the study centres employ link workers, who cover the role similar to community midwives for non-English speaking mothers. They are ideally suited to taking consent for non-English speaking mothers for this study.

It is anticipated that acceptability of the pulse oximetry test and willingness to participate in the study may potentially vary between ethnic groups. We will record baseline demographic and ethnicity information from all mothers invited to take part, including those who decline to take part, those who miss consent, or those who are later identified as ineligible. We will collect mother's hospital number, age, parity, ethnicity and language. These details will be stored anonymously. This will establish the take-up rate of the study.

By making PO a routine test in each hospital, it will become embedded in the care pathway for women post-delivery, removing the possibility that women are missed by

mistake, apathy or poor organisation. In this study, reasons for opting out will not be collected (unless it becomes apparent that this is an issue), nor will it be necessary to obtain all mothers' addresses. We anticipate a high take-up, making it unfeasible and unnecessary to collate excess information when it will be available from routine hospital data or can be collected postnatally.

All community midwives and link workers will receive training regarding the introduction of PO screening, information about the study and instruction on their roles from the local coordinating midwives. This will occur during community team meetings and the information provided will be reinforced periodically throughout the study by further meetings and newsletters from the Study Office.

3.3. Consent

The conduct of the study will be in accordance with the Medical Research Council (MRC) Guidelines for Good Clinical Practice 1998 and any subsequent amendments. The mother's written informed consent (according to usual local practice) to participate in the study must be obtained before testing. As the study is of short duration and has no consequence on the management of pregnancy or any post-natal care, the women's GP will not be notified of her participation in the study.

3.4. Organisation of Recruitment

Recruitment will be organised and supported by dedicated midwife leads, who will work with local community and antenatal clinics midwifery teams and obstetrics and neonatal leads. We believe that that the following strategy is likely to be successful in achieving maximum recruitment.

- Appointment of a dedicated coordinating midwife at each centre with responsibility for overseeing preliminary consent in the community and at the antenatal clinic of her centre, PO testing on post-natal ward and for data collection and problem resolution.
- Appointment of a lead research midwife at Birmingham Women's Hospital, who will liaise with all the coordinating midwives at each centre and coordinate the screening at this hospital, provide training and trouble-shoot recruitment and midwifery problems.
- Provision of simple written study information (similar to the "Newborn blood-spot screening" leaflet), supported by face to face discussion with midwifery staff in antenatal clinics and the community.
- Regular, close communication with midwifery staff in the community, antenatal clinic and post-natal wards.
- Training of midwifery staff on post-natal ward in obtaining PO readings, as the coordinating midwife will not be available to undertake this task on all babies.
- Provision of regular feedback on progress in study recruitment, including individual hospital teams' performance and progress against targets.
- Regular newsletters to all relevant staff involved in the study.

4. TESTS AND PROCEDURES

4.1. The index test

It is essential to explore the technical and practical aspects of conducting the PO test before the commencement of the accuracy study. A ward-based technical feasibility study will be carried out to establish the most practicable methods of testing and reporting results in the postnatal ward setting. This will also allow the development of programmes

for quality assurance and for training staff to perform PO. This will be one of the roles of the coordinating midwives.

The pulse oximeter used in the study is from the Radical® series from Masimo (Irvine CA, USA). These have been shown to outperform other oximeters in that the recording is free from motion artefact and is capable of achieving stable, accurate readings in an active subject and also when perfusion is low. Five oximeters will be available in each maternity unit in order to ensure readings can be taken at all times and to ensure readings are not missed because of faulty or misplaced machines. An oximeter will be available on both the postnatal ward and delivery suite.

The participating centres have agreed to make it standard practice to perform PO within each unit and the clinical protocols changed accordingly. PO will be performed before 24 hours or discharge, preferably at around 3-6 hours of age which corresponds to admission to the postnatal ward. PO is routinely performed on babies on the Neonatal Unit. It is painless, extremely well tolerated by babies and requires minimal clinical training. It is estimated that to perform saturations on one hand and one foot will take no more than five minutes. The results of the PO will be recorded as percentage functional saturation for each limb. The date and time of testing will also be recorded. A cut off of <95% in either limb or a difference of $\geq 3\%$ between the limb readings will be considered to be abnormal. This threshold has been shown in previous studies to have the highest sensitivity. It also has the potential to detect coarctation of aorta, a treatable condition that has been missed in earlier studies with different thresholds (14,15) It is anticipated that the maximal sensitivity of the test is achieved by about 6-12 hours of age (9;14;15), by which time we anticipate the majority of babies in this study will have been screened. If PO is low and the clinical examination is unremarkable, the PO will be repeated 1-2 hours later for a definitive definition of abnormality. If the saturations remain low, oxygen will be administered (nitrogen washout or hyperoxia test) to identify potential respiratory causes for low saturations. An echocardiogram will be performed in all case of persisting low saturations (i.e. test positive cases)

4.2. Clinical examination

Physical examination of newborns is recommended in the NICE clinical guidelines "Postnatal Care of Women and their Babies section 1.4.11' and should occur within 72 hours of birth. Assessment of the cardiovascular system should include checking the position of the heart, heart rate, rhythm and sounds, murmurs and femoral pulse volume. Each hospital will have a protocol for the timing and content of the postnatal examination and this study will not attempt to alter clinical practice, although the NICE guidelines will be promoted. The assessment is usually performed before discharge from hospital by senior house officers or registrars but may also be performed by senior midwives or advanced nurse practitioners.

Some of the participating units, in certain circumstances, defer the clinical examination, to be performed by the GP up to 10 days after birth. All GPs in the catchment areas for the participating hospitals will be informed of the study through a flyer, together with posters for the waiting room and supplies of the information leaflet. Where GPs may be called upon to perform the clinical examination, further information regarding the study will be provided in the mother's postnatal notes, together with copies of the data collection form and envelopes to return the information to the hospital.

4.3. The reference standard

The reference standard will be a combination of the following approaches.

4.3.1 Echocardiography

Echocardiography is a resource intensive procedure, and will only be undertaken on those with symptoms or signs at clinical examination (as is current practice) or those with low PO readings. Given an assumed performance of 75% sensitivity and 99.5% specificity, and an overall prevalence of 5 per 1000, in our design, we would expect 9 per 1000 to undergo echocardiography based on low saturation by PO or symptoms apparent at clinical examination and between 40-50% of these will have clinically significant CHD. Thus we anticipate between 200 and 300 extra echocardiographic examinations during the study. To enable the participating hospitals to cope with this increased demand, a specially appointed clinical research fellow will be able to visit centres to perform echocardiograms when the hospital cannot accommodate them themselves.

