6.3. Analysis for test accuracy study

The main analysis for diagnostic accuracy will include estimation of sensitivity, specificity, predictive values, likelihood ratios and their 95% confidence intervals. The baseline

characteristics of the patients enrolled in the study will be examined and planned subgroup analyses will be undertaken. Subgroup analyses are limited by statistical power and can produce spurious results particularly if many are undertaken. The recent literature review and consultation with obstetricians suggests that the accuracy of the index tests may vary according to risk factors (high risk history or antenatal suspicion on ultrasound) and timing of PO test. Therefore, secondary analyses will be limited to these subgroups only. The main and subgroup analyses are powered as outlined above based on conservative prevalence estimates. All estimates of accuracy for subgroups will be interpreted with appropriate caution.

As secondary analyses, the reference standard information obtained from echocardiography will be utilised to compare antenatal screening with PO. Such studies are commonplace in cancer research where invasive tests cannot be undertaken on those with low probability of disease. From such a design, it is possible to estimate the relative true (TPR) and false (FPR) positive rates of the two test strategies, but not the absolute sensitivity or specificity of either(39). It is also possible to estimate the trade-off between additional true positives and false positives related to the addition of PO to the standard screening programme (40). The statistical significance of the difference will be assessed using McNemar's test for paired data, and confidence intervals for the ratios computed using the methods of Cheng and Macalouso (41). The same approach can be utilised for comparing PO and clinical examination except that this analysis will be biased due to lack of blinding between the two tests. A "latent class" analysis, as described by Walter (42), will be used to estimate the sensitivity and specificity of the PO test and the antenatal screening from the screen positive study using only echocardiography as a reference standard. This approach involves an assumption of independence of test errors in the diseased and non-diseased groups, which will be tested as part of the investigation.

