APPENDIX D: PULSE OX STUDY DATA COLLECTION FORM

Section 1: Eligibility

Is the baby well? Yes No

If the baby is **well**, they are **eligible** for the study. Please ensure consent has been taken and continue with **sections 2 – 5 below**.

If the baby is **not well**, they are **not eligible** for the study. Please complete the '**Ineligibility Form**', put in the participant pack and put it in the Pulse Ox collection box. Treat the baby as normal.

Section 2: Identifying Details

Baby Hospital Number

Baby **NHS** number

Baby date of birth ____ / ____ / ____

Time (24hr) ____ : ____

Male Female

Gestational age ____ /40 weeks

Mother's Forename _____

Mother's Surname _____

Hospital Number

Mother's NHS Number

Mother's date of birth ____ / ____ / ____

(or attach sticker)

Mother's gravida ____ parity ____

Section 3: Language

Was a translator and/or a translated version of the Information Sheet and Consent required? Yes No

If yes, specify language: _____

Section 4: Pulse Oximetry Saturations

First reading (This should be taken within 24 hours of age or before discharge)

Performed in: Delivery Suite Post Natal Unit Neonatal Unit

Performed by:

PRINT NAME: _____

Doctor Nurse Midwife Midwifery Assistant Care Assistant Neonatal nurse

Date	Time	Foot sats (%)	Right hand sats (%)	% difference	Pass/Refer

If the result is normal (i.e. **Pass**), nothing further needs to be done. Please **ensure sections 1-5 are completed**. Please put this form in the participant pack and put it in the Pulse Ox collection box.

If less than 95% in either limb or $\geq 3\%$ difference between limbs, this is a **Refer**, the baby needs to be examined/ reviewed by someone trained in neonatal examination. **Please continue with section 6 overleaf**.

Section 5: Antenatal Diagnosis

Is there a family history of congenital heart defects? Yes No

Was CHD suspected on antenatal ultrasound? Yes No

The following sections only need to be completed if the first pulse oximetry reading was <95% in either limb or ≥3% difference between limbs i.e. a **Refer**.

Section 6: Clinical Examination

Undertaken by: Nurse/ Midwife SHO/ Registrar Consultant Other

How long did the exam take? _____ minutes

Did the baby show signs of CHD at examination? Yes No

If yes, was this murmur cyanosis abnormal pulses

Overall exam finding Normal Abnormal Details: _____

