If exam is normal, a second PO reading needs to be taken. This should be taken 1-2 hours after the first reading. Please complete section 7 below.

If exam is abnormal, the baby needs to be referred straight to the Neonatal team for further investigation and management. A second PO reading does not need to be taken. Please continue with sections 9-14 overleaf.

Section 7: Second Pulse Oximetry Reading

Performed in: Delivery Suite Post Natal Unit Neonatal Unit

Performed by:
PRINT NAME: _____

Doctor Nurse Midwife Midwifery Assistant Care Assistant Neonatal nurse

Date	Time	Foot sats (%)	Right hand sats (%)	% difference	Pass/Refer

*If less than 95% in either limb or ≥3% difference between limbs, this is a **Fail**, the baby needs to be referred to the Neonatal team for further investigation and management. Please continue with sections 8-14 overleaf.*

*If the result is normal (i.e. **Pass**), nothing further needs to be done. Please ensure all above sections are completed. Please put this form in the participant pack and put it in the Pulse Ox collection box.*

The following sections only need to be completed if the clinical examination found an abnormality or if the second pulse oximetry reading was a Fail and the baby has been referred to the Neonatal team for further investigation and management.

Section 8: Hyperoxia Test (only to be completed if second PO reading was a fail)

Performed by: Nurse SHO Registrar Consultant

Did saturation increase to 95% or above? Yes No

Section 9: Clinical Symptoms

If baby showed signs of CHD at birth, describe

Collapse Cyanosis Acidosis Respiratory distress

Did this baby have a respiratory illness or any illness other than CHD?

Yes No If yes details: _____

Section 10: Echocardiography

Date of echocardiography ___ / ___ / ___ Time ___ : ___ (24 Hour)

Echocardiographer: Cardiology Research Fellow Other Echocardiographer

Result: Normal Abnormal Uncertain

Details: _____

Section 11: Review of Echocardiography

Reviewed by: Cardiology Research Fellow Consultant Other

(Please tick more than one box if applicable)

Date of review ___ / ___ / ___

Result: Normal Abnormal Uncertain

Details: _____

If there is a *disagreement between the two results* or the result of the review is uncertain, a second echocardiogram needs to be performed. This will be done by a Consultant Paediatric Cardiologist at Birmingham Children's Hospital

Date of second echocardiography ___ / ___ / ___

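### The secondary comparison of PO with antenatal screening rests on echocardiography, which is neither triggered by antenatal suspicion nor required on the form after a PO pass, so the relative false-positive rate could be biased against PO

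*Protocol*

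**What the plan says.** - **Analysis (Protocol 6.3).** As secondary analyses, "the reference standard information obtained from echocardiography will be utilised to compare antenatal screening with PO". The section states that "it is possible to estimate the relative true (TPR) and false (FPR) positive rates of the two test strategies", with McNemar's test for the difference. It adds a latent-class analysis of PO and antenatal screening "from the screen positive study using only echocardiography as a reference standard".
- **Who is echoed (Protocol 4.3.1).** Echocardiography "will only be undertaken on those with symptoms or signs at clinical examination (as is current practice) or those with low PO readings". Section 4.1 adds that all babies with persisting low saturations are echoed.
- **PO-positive and PO-negative babies (Protocol 2.2).** The two groups get different reference standards: "echocardiography for the former and follow-up for the latter".
- **Form (Protocol Appendix D).** Section 5 asks of every baby "Was CHD suspected on antenatal ultrasound". Before Section 6 the form says "The following sections only need to be completed if the first pulse oximetry reading was <95% in either limb" or the limb difference is abnormal. Before Section 8 it says "The following sections only need to be completed if the clinical examination found an abnormality or if the second pulse oximetry reading was a Fail". The echo sections, 10 and 11, come after both instructions.
- **Antenatally suspected babies (Protocol 3.1.3, 4.7, 5.1, 5.4).** They are enrolled and go to a neonatal unit. Their first PO reading, clinical examination and antenatal ultrasound findings are collected, and other management is local. None of these sections mentions a planned postnatal echo.

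**The concern.** A comparison of two screening tests by a confirmatory procedure given only to screen positives can leave babies negative on both tests unverified. It cannot leave out babies positive on one test only. The reference list agrees: the titles of the cited methods papers describe confirmation confined to positives, and non-verification of those negative on both.

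Here one of the two discordant groups is covered. A PO-positive baby with a normal antenatal scan is echoed by plan. An antenatally suspected baby who passes PO is echoed only because of signs or local practice, and the form does not ask for the result. A normal echo in such a baby has no stated destination, because the separate CHD case report form is for babies with CHD.

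An analysis that counts only echo-verified babies would therefore keep every PO false positive and lose some antenatal ones. PO would look worse on false positives than it is. Section 3.1.3 gives the added value of PO over antenatal screening as a reason for enrolling these babies, and as an input to the decision model.

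**Working it through.** **1. The plan's own echo rate.** Inputs from 4.3.1: PO sensitivity 75%, specificity 99.5%, prevalence 5 per 1000.
- True positives: 1000 × 0.005 × 0.75 = 3.75 per 1000.
- False positives: 1000 × 0.995 × 0.005 = 4.975 per 1000.
- Sum: 8.725 per 1000, of which 3.75/8.725 = 43% have CHD.

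This reproduces the stated 9 per 1000 with 40-50% having CHD.

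**2. Relative false-positive rate.** Let:
- b = antenatal false-positive rate (not given);
- d = share of antenatal false positives who are also PO-positive;
- g = share of antenatal-only false positives with a recorded echo (not given).

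All PO false positives are verified. If unverified babies are excluded, the observed antenatal rate is b × [d + (1 − d)g]. The ratio PO/antenatal is then inflated by

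1 / [d + (1 − d)g],

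and b cancels. Under independent errors d = 1 − 0.995 = 0.005. Larger values of d are assumptions.

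| d | g = 100% | g = 90% | g = 50% | g = 10% |
|---|---|---|---|---|
| 0.5% | 1.00 | 1.11 | 1.99 | 9.6 |
| 5% | 1.00 | 1.10 | 1.90 | 6.9 |
| 10% | 1.00 | 1.10 | 1.82 | 5.3 |

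Example at d = 0.5%, g = 50%: 1/(0.005 + 0.995 × 0.5) = 1/0.5025 = 1.99. The protocol gives no support for a low g, so the last column is a bound. At g = 0 the ratio is in practice not estimable.

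**3. The same in counts.** Take 20,000 babies, 19,900 without CHD, and assume an antenatal false-positive rate of 0.5%, equal to that of PO.
- Each test has 19,900 × 0.005 = 99.5 false positives, so the true ratio is 1.00.
- About 0.5 are shared, so the discordant cells are 99.0 and 99.0.
- At g = 50% the antenatal-only cell falls to 49.5 and the antenatal total to 50.0. The observed ratio is 99.5/50.0 = 1.99.
- McNemar's statistic on these cells, if applied to babies without CHD, is (99.0 − 49.5)²/(99.0 + 49.5) = 16.5, although the two rates are equal.

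**4. True-positive side.** Let f be the share of antenatal-only CHD cases captured. Relative TPR is inflated by 1/(0.75 + 0.25f). Section 4.4 expects no more than 5% of late-presenting CHD to be missed. Taking f = 95% from this:
- Relative TPR: 1/0.9875 = 1.013.
- Latent-class PO sensitivity if unverified babies are dropped: 0.75/0.9875 = 76.0%, against 75%.
- With 20,000 × 0.005 = 100 CHD cases and an assumed antenatal sensitivity a of 20% to 75%, the antenatal-only cell is 25a = 5.0 to 18.75 cases. The 5% loss is 0.25 to 0.94 of a case.

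As bounds, the TPR factor is 1.14 at f = 50% and 1.33 at f = 0.

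**5. What is not touched.** Primary accuracy uses the composite standard (2.3, 4.3), and the logistic regression uses CHD status by reference standard (6.3). The extra true and false positives from adding PO come from PO-positive babies, who are echoed.

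**The case against.** The strongest reply is that the bias needs two conditions that the protocol does not state: that unverified antenatal positives are dropped, and that usual-care echoes in these babies are incomplete or unrecorded. Section 6.3 gives no rule for unverified babies, and an SAP could set one. These babies are under consultant care in a region with a specialist fetal echocardiography programme, so many may well be echoed. This stands, and it makes the bias conditional. It does not remove the point, because 6.3 itself fixes echocardiography as the information source, and no later plan can recover echo results that were not recorded.

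A reader might also draw stronger conclusions that the documents do not support:

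- *The relative FPR is certainly inflated, perhaps many-fold.* No value of g is given, and at g near 100% the effect disappears.
- *The form prevents recording these echoes.* It sets a minimum for staff. Read as a bar, it would also exclude echoes for signs in PO-pass babies, which 4.3.1 plans.
- *No echo of an antenatally suspected baby is foreseen anywhere.* Figures 1 and 2 are not reproduced and could show such a route.
- *The echo budget excludes them.* PO positives account for 174.5 of 180 echoes at 9 per 1000. The same section also expects 200 to 300 extra echoes, which leaves about 25 to 125 beyond PO positives, and usual-care echoes would not count as extra.
- *The study's main findings are at risk.* Section 2.1 assigns the comparison with antenatal screening to logistic regression, which is unaffected.

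**Conclusion.** The point holds in conditional form and is minor. Section 6.3 asks for a comparison on echocardiography information that 4.3.1, 2.2 and Appendix D do not secure for antenatal-positive, PO-negative babies. If those without a recorded echo are excluded, the relative false-positive rate is biased upward, against PO, whatever the antenatal accuracy. Allowing up to 10% of antenatal false positives to be PO-positive barely changes the result when most are echoed: the factor stays near 1.1 at g = 90% and between 1.8 and 2.0 at g = 50%. Relative TPR, McNemar's test on CHD cases and latent-class sensitivity would favour PO only slightly, because CHD in these babies should reach the cardiology unit, the register or the CHD form. The size rests on the protocol's 75% and 99.5% for PO, on an unknown g, and on reading the 5% in 4.4 as a guide to missed antenatal-only cases.

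**What to change.** 1. In 6.3, base relative TPR, relative FPR and McNemar's test for PO against antenatal screening on the one-year composite reference standard. Antenatal suspicion is already recorded for every baby in Section 5 of the form, so the full paired table is available.
2. Report the echo-only ratios and the latent-class estimates as supportive, with the share of antenatal-only positives verified by echo.
3. In Appendix D, ask for Sections 10 and 11 to be completed for any antenatally suspected baby who has an echo for any reason, whatever the PO result.

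The cost is a wording change in 6.3, one form instruction and slightly more data recording. No new echoes, babies or staff are needed. The price is reliance on follow-up for PO-negative babies. The primary analysis already accepts this, and 5.1 argues that both standards should find clinically significant CHD about equally well.
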